## 5 Statistical Methods and Determination of Sample Size

The statistical analyses will be performed under the responsibility of the Sponsor's Biostatistics platform using SAS® Version 9.4 software or later.

The results of the statistical analysis will be available in the final clinical study report (CSR).

For descriptive purposes, the following statistics will be presented:

**Table 5.1: Descriptive statistics produced**

|   |  |  |
|---|--|--|
| Baseline characteristics and follow-up description | Categorical data                      | Number of subjects.
Percentage of subjects.   |
|   | Continuous data                       | Mean, standard deviation, quartiles, minimum, and maximum.   |
| Clinical safety results                            | Categorical data                      | Solicited: Number and percentage (95% confidence interval [CI]) of subjects and number of events
Unsolicited: Number and percentage (95% CIs) of subjects and number of events.
Hospitalized VCD cases: Number and percentage (95% CIs) of subjects                                      |
| Immunogenicity results                             | Categorical data (cutoff)             | Number and percentage (95% CIs) of subjects.   |
|   | Continuous data (titer / titer ratio) | $\log_{10}$ : Mean and standard deviation.
Anti- $\log_{10}$ (work on $\log_{10}$ distribution, and anti- $\log_{10}$ applied): Geometric mean, 95% CI of the geometric mean, quartiles, minimum, and maximum.
Graphical representation by Reverse Cumulative Distribution Curve (RCDC). |

The CI for the single proportion will be calculated using the exact binomial method (Clopper-Pearson method, quoted by Newcombe (1), i.e., using the inverse of the beta integral with SAS®).

For immunogenicity, assuming that  $\log_{10}$  transformation of the titers follows a normal distribution, at first, the mean and the 95% CI will be calculated on  $\log_{10}$  titers using the usual calculation for normal distribution (using Student's t distribution with n-1 degree of freedom), then antilog transformations will be applied to the results of calculations, in order to provide geometric means (GMs) and their 95% CI.

GM is defined as follows:

$$GM = \left( \prod_{i=1}^n y_i \right)^{1/n} = 10^{\hat{\left( \frac{1}{n} \sum_{i=1}^n \log_{10}(y_i) \right)}}$$

where  $(y_1, y_2, \dots, y_n)$  are the observed titers or other data where applicable for each subject.

## 5.1 Statistical Methods

In a general way, non-inferiority testing will be performed on dengue immune subjects. The tests will be done only if the number of evaluable subjects provides a global power of at least 80% for the co-primary objectives and secondary objective. In case the global power is insufficient to perform non-inferiority testing, only descriptive analyses will be performed.

Only descriptive analyses will be conducted in dengue non-immune subjects and in the overall population.

### 5.1.1 Hypotheses and Statistical Methods for Primary Objectives

#### 5.1.1.1 Hypotheses

##### *Non-inferiority on Gardasil*

The objective is to demonstrate that the humoral immune response to Gardasil administered concomitantly with CYD dengue vaccine is non-inferior to the immune response to Gardasil administered sequentially with CYD dengue vaccine.

##### Individual hypotheses on Gardasil response for each antigen:

A non-inferiority testing approach will be used to compare geometric mean of titer (GMTs) for the 4 antigens (HPV-6, HPV-11, HPV-16, HPV-18) 28 days after the last dose of Gardasil, based on the following individual hypotheses:

$$H_0^i: \text{GMT}_{\text{Group1}}^i / \text{GMT}_{\text{Group2}}^i \leq \frac{1}{\delta} \Leftrightarrow \log_{10}(\text{GMT}_{\text{Group1}}^i) - \log_{10}(\text{GMT}_{\text{Group2}}^i) \leq -\log_{10}(\delta)$$

$$H_1^i: \frac{1}{\delta} < \text{GMT}_{\text{Group1}}^i / \text{GMT}_{\text{Group2}}^i > \frac{1}{\delta} \Leftrightarrow \log_{10}(\text{GMT}_{\text{Group1}}^i) - \log_{10}(\text{GMT}_{\text{Group2}}^i) > -\log_{10}(\delta)$$

with:

i, antigen (HPV-6, HPV-11, HPV-16, HPV-18)

$\delta$  non-inferiority limit is set at 2, ie, 0.301 ( $=\log_{10}[2]$ ), for each antigen "i"

Non-inferiority for antigen i will be demonstrated if the lower bound of the 2-sided 95% CI is greater than  $-\delta$  ( $\alpha=2.5\%$  one-sided).

##### Global hypotheses for non-inferiority on Gardasil response:

The global hypotheses are:

$H_{0G}$ : Non inferiority of Gardasil co-administered with CYD dengue vaccine versus Gardasil administered sequentially with CYD dengue vaccine is not demonstrated for at least one antigen.

$H_{1G}$ : Non-inferiority of Gardasil co-administered with CYD dengue vaccine versus Gardasil administered sequentially with CYD dengue vaccine is demonstrated for all the antigens.

$H_0^G$  : at least one  $H_0^i$  not rejected

$H_1^G$  : all  $H_0^i$  are rejected

### ***Non-inferiority on CYD Dengue Vaccine***

The objective is to demonstrate that the humoral immune response to the CYD dengue vaccine administered concomitantly with Gardasil is non-inferior to the immune response to CYD dengue vaccine administered sequentially with Gardasil.

#### **Individual hypotheses on CYD response for each antigen:**

A non-inferiority testing approach will be used to compare GMTs 28 days after the third injection of CYD dengue vaccine between groups for each serotype “i” based on the following individual hypotheses:

$$H_0^i: \text{GMT}_{\text{Group1}}^i / \text{GMT}_{\text{Group2}}^i \leq \frac{1}{\delta} \Leftrightarrow \log_{10}(\text{GMT}_{\text{Group1}}^i) - \log_{10}(\text{GMT}_{\text{Group2}}^i) \leq -\log_{10}(\delta)$$

$$H_1^i: \frac{1}{\delta} < \text{GMT}_{\text{Group1}}^i / \text{GMT}_{\text{Group2}}^i > \frac{1}{\delta} \Leftrightarrow \log_{10}(\text{GMT}_{\text{Group1}}^i) - \log_{10}(\text{GMT}_{\text{Group2}}^i) > -\log_{10}(\delta)$$

with:

i, serotypes in {1, 2, 3, 4}

$\delta$  non-inferiority limit is set at 2 ie, 0.301 ( $=\log_{10}[2]$ ), for each serotype “i”

Non-inferiority for serotype i will be demonstrated if the lower bound of the 2-sided 95% CI is greater than  $-\delta$ .

#### **Global hypotheses for non-inferiority on CYD response:**

$H_0^G: \text{at least one } H_0^i \text{ not rejected}$

$H_1^G: \text{all } H_0^i \text{ are rejected}$

Overall, non-inferiority among the groups will be demonstrated if, for each antigen of Gardasil and each serotype of CYD dengue vaccine, the 2-sided 95% CIs lie above  $-\delta$ .

#### **5.1.1.2 Statistical Methods**

The non-inferiority test will be performed using the 95% 2-sided CI of the difference of the means of the  $\log_{10}$  transformed post- vaccination titers between Group 1 and Group 2 ( $\alpha=2.5\%$  one-sided). The CI for differences will be calculated using normal approximation of log-transformed titers.

#### **5.1.2 Hypotheses and Statistical Methods for Secondary Objectives**

##### **5.1.2.1 Hypotheses**

###### ***Non-inferiority on Gardasil***

The objective is to demonstrate that the humoral immune response (in terms of seroconversion) to Gardasil after concomitant administration with CYD dengue vaccine is non-inferior to sequential administration with CYD dengue vaccine measured 28 days after the last dose of Gardasil.

A non-inferiority testing approach will be used to compare seroconversion rates for the 4 antigens (HPV-6, HPV-11, HPV-16, HPV-18) 28 days after the last dose of Gardasil.

The individual tested hypotheses for the antigen “i” will be as follows:

$$H_0^i: P_{Group1}^i - P_{Group2}^i \leq -\delta$$

$$H_1^i: P_{Group1}^i - P_{Group2}^i > -\delta$$

where the non-inferiority limit  $\delta$  is set at 5% for each antigen “i”.

#### ***Non-inferiority on CYD dengue vaccine***

No statistical hypothesis will be tested on CYD dengue vaccine for secondary objectives.

#### **5.1.2.2 Statistical Methods**

##### ***Non-inferiority on Gardasil***

Non-inferiority for antigen “i” will be demonstrated if the lower bound of the 2-sided 95% CI is greater than  $-\delta$ .

The non-inferiority test will be performed using the 95% 2-sided CI of the difference between groups ( $\alpha=2.5\%$  one-sided). The 95% CI will be calculated based on the Wilson score method without continuity correction as quoted by Newcombe for seroconversion rates.

##### ***Descriptive analysis on Gardasil and CYD dengue vaccine immunogenicity***

No hypotheses will be tested.

Immunogenicity point estimates and their 95% CI will be presented for each and any group, at baseline and after each dose of Gardasil and CYD dengue vaccine.

A complementary analysis on CYD dengue vaccine immunogenicity after each dose will be conducted for each and any group according to the dengue status at baseline (dengue immune, dengue non-immune, and all subjects).

The 95% CIs will be calculated using:

- The normal approximate method for GMTs and GMTRs  
Assuming that  $\log_{10}$  transformation of the titers / data follows a normal distribution, at first, the mean and the 95% CI will be calculated on  $\log_{10}$  (titers / data) using the usual calculation for normal distribution (using Student’s t distribution with  $n-1$  degree of freedom), then antilog transformations will be applied to the results of calculations, in order to provide geometric means (GMs) and their 95% CI.
- The exact binomial distribution for single proportions (Clopper-Pearson’s method, quoted by Newcombe)

##### ***Safety***

All analyses will be descriptive; no hypotheses will be tested. Safety will be assessed for all subjects and for immune subjects after each and any dose of Gardasil and CYD Dengue vaccine. Moreover, a complementary analysis will be performed for each dose of CYD dengue vaccine, for each and any group, on non-immune subjects.

As there are differences in the intensity considered for measurable reactions depending on ages of subjects, a complementary analysis will be performed according to the following age groups: 9-11 years and 12 to 13 years.

For the main parameters, 95% CIs of point estimates will be calculated using the normal approximation for quantitative data and the exact binomial distribution (Clopper-Pearson method, quoted by Newcombe) for single proportions.

## 5.2 Analysis Sets

Four analysis sets will be used: the Per-Protocol analysis set for Gardasil (PPG), the Per-Protocol analysis set for CYD Dengue Vaccine (PPC), the Full Analysis Set (FAS) and the Safety Analysis Set (SafAS).

### 5.2.1 Full Analysis Set

The Full Analysis Set (FAS) is defined as the subset of subjects who received at least one dose of the study vaccines.

Subjects will be analyzed by baseline dengue status and the vaccine treatment group to which they were randomized.

### 5.2.2 Per-Protocol Analysis Set

Two per-protocol analysis sets will be defined: one for Gardasil (PPG) and one for CYD dengue vaccine (PPC). The per-protocol analysis sets are subsets of the FAS.

#### **PPG**

The subjects presenting with at least one of the following relevant protocol deviations will be excluded from the PPG:

- Subject did not meet all protocol-specified inclusion criteria or met at least one of the protocol-specified exclusion criteria
- Subjects identified as dengue non-immune subjects (seronegative) at baseline
- Subject is seropositive at baseline for Gardasil (ie, at least one Ab levels against Gardasil HPV antigens > LLOQ at baseline)
- Subject did not complete the Gardasil vaccination schedule (until V05)
- Subject received a vaccine other than the one that she was randomized to receive (until V05 for Group 1, V06 for Group 2)
- Administration of vaccine was not done as per-protocol (site and route of administration) (until V05)
- Subject did not receive vaccine in the proper time window (until V05 for Group 1, V06 for Group 2)
- Subject did not provide after the 2nd dose of Gardasil a post-dose serology sample in the proper time window or a post-dose serology sample was not drawn (V05 for Group 1, V06 for Group 2)

- Subject received a protocol-prohibited medication (prohibited therapies/ medications/ vaccines are indicated in the Protocol Section 6.7) (until V05 for Group 1, V06 for Group 2)
- Subject's serology sample after the 2nd dose of Gardasil did not produce a valid test result, ie, no Gardasil antigen titer available (V05 for Group 1, V06 for Group 2)

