12.2.2 Per-Protocol Analysis Set

Two PPASs will be defined: one for Gardasil (PPG) and one for the CYD dengue vaccine (PPC). The PPASs are subsets of the FAS.

PPG

The subjects presenting with at least one of the following relevant protocol deviations will be excluded from the PPG:

- Subject did not meet all protocol-specified inclusion criteria or met at least one of the protocol-specified exclusion criteria
- Subjects identified as dengue unexposed (seronegative) at baseline
- Subject is seropositive at baseline for Gardasil (i.e., at least one Ab levels against Gardasil HPV antigens > LLOQ at baseline)

- Subject did not complete the vaccination schedule (until V05)
- Subject received a vaccine other than the one that he/she was randomized to receive (until V05 for Group 1, V06 for Group 2)
- Administration of vaccines was not done as per-protocol (site and route of administration) (until V05)
- Subject did not receive vaccines in the proper time window (until V05 for Group 1, V06 for Group 2)
- Subject did not provide after the 2nd dose of Gardasil a post-dose serology sample in the proper time window or a post-dose serology sample was not drawn (until V05 for Group 1, V06 for Group 2)
- Subject received a protocol-prohibited medication (prohibited therapies / medications / vaccines are indicated in Section 6.7) (until V05 for Group 1, V06 for Group 2)
- Subject's serology sample after the 2nd dose of Gardasil did not produce a valid test result, i.e., no Gardasil antigen titer available (until V05 for Group 1, V06 for Group 2)

PPC

The subjects presenting with at least one of the following relevant protocol deviations will be excluded from the PPC:

- Subject did not meet all protocol-specified inclusion criteria or met at least one of the protocol-specified exclusion criteria
- Subjects identified as dengue unexposed (seronegative) at baseline
- Subject did not complete the vaccination schedule
- Subject received a vaccine other than the one that he/she was randomized to receive
- Administration of vaccines was not done as per-protocol (site and route of administration)
- Subject did not receive vaccines in the proper time window
- Subject did not provide after the 3rd dose of the CYD dengue vaccine a post-dose serology sample in the proper time window or a post-dose serology sample was not drawn (V08, M13 for Group 1 and M14 for Group 2)

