### 3 Description of the Overall Trial Design and Plan

#### 3.1 Trial Design

This is a Phase IIIb, randomized, open-label, multicenter study in 528 subjects aged 9 to 13 years in Malaysia.

Subjects have been randomized in a 1:1 ratio into one of 2 following groups, stratified by gender in a 2:1 (female:male) ratio to receive:

- Group 1 (N=264): 3 doses of CYD dengue vaccine and 2 doses of Gardasil® (Human Papillomavirus Quadrivalent [Types 6, 11, 16, and 18] Vaccine, Recombinant) concomitantly to the first 2 doses of CYD dengue vaccine
- Group 2 (N=264): 3 doses of CYD dengue vaccine and 2 doses of Gardasil sequentially to the first 2 doses of CYD dengue vaccine

For both vaccines, each dose is to be administered 6 months apart.

As per Protocol Amendment 1, only subjects identified as dengue immune (seropositive) before administration of the first CYD dengue injection (at V01 for Group 1 and at V02 for Group 2) and who consented to receive the remaining injection of dengue vaccine could remain in the study as per initial study procedures.

Subjects identified as non-immune (seronegative) at baseline could continue in the study for a 6-month safety follow-up. They did not receive any further CYD dengue vaccine injection and had a blood sample for the assessment of HPV antibodies after the 2 doses of Gardasil if they returned in study for M7 (Visit 5).

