## 5.5 Determination of Sample Size and Power Calculation

A total of 528 subjects was enrolled: 264 subjects in each group.

The reference standard deviations (SD) considered are the following for Gardasil: 0.6, 0.4, 0.5 and 0.5 for HPV-6, HPV-11, HPV-16 and HPV-18, respectively.

The reference seroconversion rates for Gardasil were set to 99% for all of the 4 antigens.

The reference SD considered are the following for the CYD dengue vaccine: 0.7 for serotypes 1 and 2, 0.5 for serotypes 3 and 4 (based on CYD studies conducted in Asia Pacific: CYD14, CYD23, CYD22 and CYD28).

Considering a potential attrition rate of 15%, such sample size would provide 222 evaluable subjects per group in the PPAs. This will give, for the co-primary objectives, a global power of 98.4% and for secondary objectives (in terms of Gardasil seroconversion) a power of 90.2%.

Following Protocol Amendment 1, the number of evaluable subjects may be difficult to achieve (considering only exposed/seropositive subjects at baseline to be included in the Per-Protocol populations). Thus the non-inferiority testing will be done only if the number of evaluable subjects provides a global power of at least 80% for the co-primary objectives and secondary objective i.e., if the number of evaluable subjects per group is at least 121 per group for the co-primary objectives and 194 per group for the secondary objective. The power for non-inferiority in terms of GMTs per antigen and serotype will be than as follows:

This sample size will also provide a 95% probability of observing an AE that has a true incidence of 1.1% in each group.

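### One positive HPV type at baseline removes a child from all four main Gardasil tests, which matters chiefly for reaching the 194 per group needed for the seroconversion test

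*SAP*

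**What the plan says.** SAP 5.2.2 lists among the reasons for exclusion from the PPG: "Subject is seropositive at baseline for Gardasil (ie, at least one Ab levels against Gardasil HPV antigens > LLOQ at baseline". Protocol 12.2.2 has the same rule ("at least one Ab levels against Gardasil HPV antigens > LLOQ at baseline"), and the statistical methods part of the protocol synopsis repeats it. One PPG serves the main tests of all four HPV antigens. Neither document gives a reason for excluding on any type, and no antigen-specific set is defined.

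The rest of the Gardasil analysis is specific to the antigen. SAP 5.1.1.1 and 5.1.2.1 state a hypothesis for each antigen and judge each by its own confidence interval; SAP Tables 5.2 and 5.3 give power by antigen. The global Gardasil hypothesis then requires all four to succeed.

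After Amendment 1, testing depends on the number evaluable. SAP 5.5 requires "at least 121 per group for the co-primary objectives and 194 per group for the secondary objective", ties the evaluable number to the per-protocol populations, and warns that "the number of evaluable subjects may be difficult to achieve". Below the minimum, the analysis is descriptive only.

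Two provisions soften the rule. SAP 5.2.5 confirms the non-inferiority tests on dengue-immune FAS subjects, with no HPV baseline exclusion. The dengue per-protocol set (PPC) has no such exclusion either.

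**The concern.** A child above the LLOQ for HPV-6 alone is seronegative at baseline for HPV-11, HPV-16 and HPV-18. The responses to those three types start from a negative baseline, yet the main tests do not use them. The usual reason for such an exclusion, that pre-existing antibody blurs the response to the vaccine, applies directly only to the type for which the child is positive.

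A common set is not needed to keep the denominators equal. A child leaves the PPG for an invalid result only when no HPV titre at all is available, so numbers can already differ by antigen.

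What is at stake is whether the secondary seroconversion objective is tested or only described. Its minimum of 194 is 194/264 = 73.5% of those enrolled per group and 194/222 = 87.4% of the number planned as evaluable, and the PPG is now confined to dengue-immune children. A modest extra loss could decide the matter if the count falls close to 194.

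**Working it through.** **Inputs from the documents.** 264 enrolled and 222 planned evaluable per group; minimum 121 (GMT) and 194 (seroconversion); one-sided alpha 2.5%; seroconversion 99% in both groups with a 5-point margin; GMT margin 0.301 log10; SDs 0.6, 0.4, 0.5, 0.5 (HPV-6, 11, 16, 18) and 0.7, 0.7, 0.5, 0.5 (dengue 1 to 4). All are in SAP 5.1 and 5.5.

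**Assumed, not in the documents.** Baseline positivity p per HPV type (0.5% to 5%, equal across types), and 200 children per group who are otherwise evaluable.

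**Step 1: reproduce the 194.** Farrington–Manning score formula: power = Φ[(0.05 − 1.96·s0)/s1], with s1 = √(2 × 0.99 × 0.01/n) and s0 = √{[a(1−a) + b(1−b)]/n}. Here a = 0.9446 and b = 0.9946 are the rates fitted under a difference of −0.05.
- n = 194: s0 = 0.01724, s1 = 0.01010, power 94.6% per antigen; to the fourth power, 80.0%.
- n = 193: 94.4% and 79.5%.
- n = 222: 97.4% and 90.2%.

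These match SAP Table 5.3, and 194 is the smallest n that reaches 80%. The planned interval is the Newcombe one, for which an exact calculation at 194 gives 96.2% per antigen and 85.6% global. Because the plan fixes 194 as a count, this does not change the comparison below.

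**Step 2: see what limits the 121.** Noncentral t, with endpoints multiplied as independent. At 121 per group the four HPV tests have joint power 96.6% and the four dengue tests 83.1%; the product is 80.3%, against 80.4% in SAP Table 5.2. Serotypes 1 and 2, at 91.5% each, account for most of the shortfall, and they are analysed in the PPC. Varying the two sets separately:
- PPG 115 with PPC 130: 82.8%.
- PPG 126 with PPC 115: 78.2%.

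A smaller PPG therefore need not bring global power below 80%, and a larger one does not rescue a small PPC.

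**Step 3: the loss from the any-type rule.** With independent types the any-type rule removes 1 − (1−p)^4; an antigen-specific rule removes p for each antigen. Starting from 200 per group, rounding down, with global seroconversion power by the formula of step 1:

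| p per type | Lost, any-type | Left, any-type (power) | Left, antigen-specific (power) |
|---|---|---|---|
| 0.5% | 2.0% | 196 (80.9%) | 199 (82.3%) |
| 1% | 3.9% | 192 (79.0%) | 198 (81.8%) |
| 2% | 7.8% | 184 (74.8%) | 196 (80.9%) |
| 3% | 11.5% | 177 (70.6%) | 194 (80.0%) |
| 5% | 18.5% | 162 (60.2%) | 190 (78.0%) |

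These are expected counts. At 3% the antigen-specific figure sits exactly on 194, so by chance the smallest of the four could still miss it.

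**Step 4: how close to 194 the count must be.** Otherwise evaluable children per group needed to keep 194 are 194/(1−p)^4 under the plan and 194/(1−p) under the alternative, rounded up: 202 against 196 at 1%, 211 against 198 at 2%, 220 against 200 at 3%. The choice of rule decides the test only between those pairs.

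**Step 5: overlap.** If the same children are positive for all four types, both rules remove the share p and the counts are equal. Real overlap would lie between this and independence.

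**The case against.** The rule is explicit, prespecified and the same in the synopsis, protocol and SAP, so it is a choice of analysis and not an inconsistency. The entry criteria treat HPV exposure at the level of the child, without regard to type, and the global hypothesis needs all four antigens, so a single all-types-naive population is coherent. All of this stands. It makes the rule defensible, but it does not show that the any-type form is needed.

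A reader might infer that valid responses are discarded from the trial. They are not: the FAS-immune confirmation keeps them. That analysis only supports the main test, however, and SAP 5.5 counts evaluable subjects in the per-protocol populations, so it does not help if the count falls short.

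A reader might also infer that the GMT tests are endangered through the 121. Read as a bare head-count of the PPG, it could be missed. Read as the 80% global power it stands for, it depends mostly on dengue serotypes 1 and 2 in the PPC, as step 2 shows.

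Nor do the documents support a claim that the rule will cost the seroconversion test. They give no seroprevalence; reported HPV history and prior HPV vaccination bar entry; the 15% attrition may already allow for these exclusions; and the plan attributes its difficulty to dengue serostatus. Against this, the HPV history is as reported, with no serological screening before enrolment, so undetected positives can enter, and the PPG rule itself provides for them.

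Finally, the four-fold-rise branch of the seroconversion definition is no argument either way: an antigen-specific exclusion would leave it equally unused in the main analysis.

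**Conclusion.** The point holds as a low-cost improvement to the main PPG analysis, not as an error. Excluding on any type removes baseline-negative responses from up to three of the four main HPV comparisons for each affected child, without a stated reason. HPV antibody at baseline is measured at D0 before any vaccination in both groups, so an antigen-specific exclusion leaves the randomised comparison intact, and it can never give fewer evaluable subjects for any antigen.

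The consequence is confined in practice to the 194 per group for seroconversion. With 200 otherwise evaluable per group and independent types, 1% positivity per type is enough to separate the rules (192 against 198). At 0.5% both meet the minimum; at 5% both fail (162 against 190). These figures rest on an assumed prevalence, an assumed starting number and independence. With full overlap between types the gain is zero, so the true benefit may be small.

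**What to change.** Before database lock, replace the bullet in SAP 5.2.2 and protocol 12.2.2 with wording such as: *for antigen i, subjects with baseline antibody to antigen i above the LLOQ are excluded from the analysis of antigen i only*. Apply the minimum number to the smallest of the four antigen-specific counts in each group. Setting it separately for each antigen would leave no rule when some pass and others fail, while the global hypothesis needs all four. Keep the all-types-naive PPG as a supportive analysis, and report by group how many children each rule excludes. If the any-type rule is kept, state the reason.

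The cost is a change of wording and four denominators in place of one. The downside is that numbers differ by antigen, and if the assay shows cross-reaction between types, those types may need to be handled as a pair.
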